The reported Overall Intracranial Response Rate (CR+PR) in a subgroup of 109 patients with untreated BM was 7% (95%CI: 3-14) compared to an extracranial Response Rate of 53% (95% CI: 43-63). Out of these 109 patients, 22 presented with BM qualifying for target lesion following RECIST 1.1. The OIRR in these 22 patients was 18% (95% CI: 4-40). In the subgroup of 109 patients with untreated BM at baseline, the intracranial disease control rate at 12 weeks was reported at 56% (95% CI: 46-66) and the median duration of intracranial response was 26.4 weeks (95% CI: 4.9 to 59.3 weeks). The systemic disease control rate at 12 weeks in this group was reported at 63% (95% CI: 54-72) and the median duration of systemic response was 47.9 weeks (95% CI: 5.3 to 55.0 weeks).

Leptomeningeal carcinomatosis (LC) is a rare devastating disease resulting from the seeding of malignant cells to the leptomeninges and cerebrospinal fluid (CSF). LC is observed in approximately 5% of the patients diagnosed with metastatic NSCLC ([Chamberlain 2010](#)). The incidence of LC in ALK-positive NSCLC may be around 5 to 6% ([Gainor et al 2013](#)). Median survival without treatment is about 4-6 weeks and about 4 months with the available treatments (whole brain radiation therapy and intrathecal chemotherapy) ([Lee 2013](#), [Palma 2013](#)). The role of systemic treatment for LC has not been established. Case reports and small series of subjects indicate that LC control may be observed with the use of highly active targeted therapies like EGFR TKI ([Lee et al 2013](#)) or ALK TKI ([Riess 2013](#), [Ahn 2012](#)).

[figure not shown]
There is a medical need for more effective treatment for patients with ALK-positive NSCLC metastatic to the CNS before and after failure to crizotinib.

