ALK, a receptor tyrosine kinase, is involved in the genesis of several cancers through genetic aberrations involving translocation of the kinase domain with multiple fusion partners or activating mutations in the full-length receptor that result in ligand-independent constitutive activation. ALK rearrangement and EGFR mutation are known to be mutually exclusive in NSCLC. Similarly to what is observed with mutated EGFR in NSCLC, ALK rearrangements constitute a key and strong oncogenic driver for NSCLC and represent a critical target susceptible to targeted ALK inhibition. The inhibition of ALK translates into the control of the NSCLC. Crizotinib, the first ALK inhibitor to be evaluated in advanced or metastatic ALK-positive NSCLC patients after failure to a prior platinum-based chemotherapy, achieves a higher response rate (RR) (65%; 95%CI: 58-72) and a longer progression free survival (PFS) compared with second-line chemotherapy (7.7 months versus 3.0 months, HR=0.49; 95% CI, 0.37 – 0.64) (Shaw et al 2013).

Crizotinib may have clinical activity in patients with ALK positive NSCLC metastatic to the brain, but its activity may be less remarkable in the brain than systemically (outside of the brain). Costa et al (2012) measured the concentration of crizotinib in both CSF and plasma and reported that the CSF-to-plasma ratio of crizotinib was 0.0026. Shaw et al (2013) evaluated the progression free survival in a subgroup of patients with or without BM at baseline. The hazard ratio still favored crizotinib compared to second-line chemotherapy in patients with BM (HR=0.67; 95%CI: 0.44 – 1.03) but the results for the subgroup of patients without BM (HR=0.43; 95% CI, 0.30 – 0.60) suggest that crizotinib may not easily cross the blood brain barrier. Crizotinib does not prevent the onset of brain metastases - the brain is the first site of progression in 46% of patients with ALK-positive crizotinib-treated NSCLC (Otterson et al 2012). Another indication that crizotinib has lesser clinical activity in the brain is demonstrated in the low Overall Intracranial Response Rate (OIRR - CR+PR) reported in a group of 109 patients with ALK positive NSCLC with untreated brain metastases at baseline. The OIRR is 7% (95%CI: 3-14) compared to an extracranial Response Rate of 49% (95%CI: 43-63) The OIRR across 22 patients out of the 109, who presented with measurable brain lesion at baseline is 18% (95% CI: 4-40) (Crino et al 2013).

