10.9 Power for analysis of key secondary variables

Estimation of the DCR is the key secondary objective of the study. An observed DCR of 65% in 140 patients in Arms 1-4 will result in an exact binomial 95% CI with a lower bound greater than 55%. [Table 10-2](#) provides the exact binomial 95% CI for various observed DCRs for the 140 patients and for each of the strata.

Table 10-2 Exact binomial 95% confidence intervals for various observed DCRs

Sample Size	Observed DCR	Number of Patients with SD, PR or CR	Exact 95% CI
N=140 (overall Arms 1-4)	65%	91	(56.49%, 72.86%)
	75%	105	(66.98%, 81.93%)
N=80 (Arms 1 and 2)	60%	48	(48.44%, 70.80%)
	70%	56	(58.72%, 79.74%)
N=40 (each of Arms 1 or 2)	60%	24	(43.33%, 75.14%)
	70%	28	(53.47%, 83.44%)
N=30 (each of Arms 3 or 4)	70%	21	(50.60%, 85.27%)
	80%	24	(61.43%, 92.29%)

An additional secondary objective of the study is estimation of the OIRR for patients with measurable brain metastases at baseline. As described in [Section 4.1.1](#), the study targets enrolling approximately 70 patients with measurable brain metastases: ~50 patients with prior ALKi treatment (Arms 1 and 2) and ~20 patients with no prior ALKi treatment (Arms 3 and 4). An observed OIRR of 50% in 70 patients with measurable brain metastases in Arms 1-4 will result in an exact binomial 95% CI with a lower bound greater than 35%. An observed OIRR of 60% in 50 patients with measurable brain metastases previously treated with and ALKi (Arms 1 and 2) will result in an exact binomial 95% CI with a lower bound greater than 45%. An observed OIRR of 60% in 20 patients with measurable brain metastases not previously treated with and ALKi (Arms 3 and 4) will result in an exact binomial 95% CI with a lower bound greater than 36%. The reported OIRR with Crizotinib is 18% (95% CI: 5 - 40) for patients with measurable brain metastases and prior radiation therapy to the brain, and 33% (95% CI: 13 - 59) for patients without prior radiation to the brain; recent whole brain radiation was allowed ([Crino et al 2013](#)).

Table 10-3 Exact binomial 95% confidence intervals for various observed OIRRs

	Observed OIRR	Number of Patients with Confirmed PR or CR in the brain	Exact 95% CI
N=70 (Overall Arms 1-4)	45%	32	(33.74%, 58.06%)
	50%	35	(37.80%, 62.20%)
	55%	39	(43.34%, 67.59%)
	60%	42	(47.59%, 71.53%)
N=50 (prior ALKi treatment, Arms 1+2)	40%	20	(26.41 %, 54.82 %)
	45%	23	(31.81 %, 60.68 %)
	50%	25	(35.53%, 64.47%)
	55%	28	(41.25%, 70.01%)
	60%	30	(45.18%, 73.59%)

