#### 2.8.1.2.1 Intracranial endpoints

**Overall intracranial response rate (OIRR):** OIRR is calculated based on response assessments in the brain for patients having measurable brain metastases at baseline. The OIRR is defined as the proportion of patients with a best overall confirmed response of CR or PR in the brain as assessed per modified RECIST 1.1.

OIRR will be estimated and the exact binomial 95% CI will be presented by study arm and for all patients. OIRR will also be summarized by prior radiotherapy to the brain (yes, no) and prior ALK inhibitor use (yes, no) and overall using the data from Arms 1 through 4. OIRR by the investigator and by BIRC will be summarized separately.

Same analysis on OIRR will be conducted for patients having evaluable (measurable or non-measurable) brain metastases at baseline.

**Intracranial disease control rate (IDCR) at 8 and 16 weeks and overall:** IDCR is calculated based on response assessments in the brain for patients having evaluable (measurable or non-measurable) brain metastases at baseline. In what follows, CR, PR and SD are possible responses only for patients with measurable brain metastases at baseline, while non-CR/non-PD is a possible response only for patients without measurable brain metastases at baseline.

- The IDCR at 8 and 16 weeks is defined as the proportion of patients with CR, PR, SD or non-CR/non-PD assessment in the brain at Week 8 and Week 16 intracranial tumor evaluations respectively, taking into consideration 4-week window for each assessment, i.e., assessment done between study day 29 and 85 (both inclusive) for week 8 and study day 86 and 141 (both inclusive) for week 16, as per modified RECIST 1.1. If there are multiple tumor assessments within the defined window, the following rules should be used hierarchically to select the overall response contributing to the xx-week IDCR rate:
  - 1) PD - If at least one tumor assessment with overall response of PD;
  - 2) Unknown - if all tumor assessment with overall responses of unknown;

3) CR/PR/SD - Overall response from the latest tumor assessment within the window

The assessment of SD too early or PD too late will be considered as Unknown and following the same rule specified in SAP [Section 2.7.1](#).

- IDCR overall is defined as the proportion of patients with a best overall response of CR, PR, SD or non-CR/non-PD in the brain, as assessed per modified RECIST 1.1.

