**Table 2-5 Exact binomial 95% confidence intervals for various observed DCRs**

Sample Size	Observed DCR	Number of Patients with SD, PR or CR	Exact 95% CI
N=140 (overall Arms 1-4)	65%	91	(56.49%, 72.86%)
	75%	105	(66.98%, 81.93%)
N=80 (Arms 1 and 2)	60%	48	(48.44%, 70.80%)
	70%	56	(58.72%, 79.74%)
N=40 (each of Arms 1 or 2)	60%	24	(43.33%, 75.14%)
	70%	28	(53.47%, 83.44%)
N=30 (each of Arms 3 or 4)	70%	21	(50.60%, 85.27%)
	80%	24	(61.43%, 92.29%)

An additional secondary objective of the study is estimation of the OIRR for patients with measurable brain metastases at baseline. As described in [Section 4.1.1 of the study protocol](#), the study targets enrolling approximately 70 patients with measurable brain metastases: ~50 patients with prior ALKi treatment (Arms 1 and 2) and ~20 patients with no prior ALKi treatment (Arms 3 and 4). An observed OIRR of 50% in 70 patients with measurable brain metastases will result in an exact binomial 95% CI with a lower bound greater than 35%. An observed OIRR of 60% in 50 patients with measurable brain metastases previously treated with ALKi (Arms 1 and 2) will result in an exact binomial 95% CI with a lower bound greater than 45%. An observed OIRR of 60% in 20 patients with measurable brain metastases not previously treated with ALKi (Arms 3 and 4) will result in an exact binomial 95% CI with a lower bound greater than 36% ([Table 2-6](#)). The reported OIRR with crizotinib is 18% (95% CI: 5 - 40) for patients with measurable brain metastases and prior radiation therapy to the brain, and 33% (95% CI: 13 - 59) for patients without prior radiation to the brain; recent whole brain radiation was allowed ([Crino et al 2013](#)).

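### Does the conflicting radiation label on the 18% crizotinib intracranial response rate call for a change to the plan?

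*Protocol*

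**What the plan says.** Protocol 10.9 states the precision expected for the overall intracranial response rate (OIRR) in patients with measurable brain metastases, then adds a historical figure: "The reported OIRR with Crizotinib is 18% (95% CI: 5 - 40) for patients with measurable brain metastases and prior radiation therapy". The same sentence gives 33% (13 to 59) for "patients without prior radiation to the brain; recent whole brain radiation was allowed". SAP 2.10 carries the sentence over: "The reported OIRR with crizotinib is 18% (95% CI: 5 - 40) for patients with measurable brain metastases and prior radiation therapy".

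The background sections cite the same report. Protocol 1.1.3 describes 109 patients with untreated brain metastases, 22 of whom had lesions that qualified as targets: "The OIRR in these 22 patients was 18% (95% CI: 4-40"). Protocol 2.1 describes the same "group of 109 patients with ALK positive NSCLC with untreated brain metastases at baseline" and repeats 18% (4 to 40) for the 22.

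The extracranial rate for the 109 also differs. Protocol 1.1.3 has "compared to an extracranial Response Rate of 53% (95% CI: 43-63"); Protocol 2.1 has "compared to an extracranial Response Rate of 49% (95%CI: 43-63").

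On the trial's own analysis, SAP 2.8.1.2.1 says that "OIRR will also be summarized by prior radiotherapy to the brain (yes, no"), and SAP 2.7.2 says that the study is for estimation and that no hypothesis will be tested.

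**The concern.** The same 18% is assigned to irradiated patients in the sample-size sections and to patients with untreated metastases in the background. On the natural reading of untreated, these are opposite groups. The remark about recent whole brain radiation makes it worse, because it follows directly on the group said to have had none.

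The trial reports OIRR by prior brain radiotherapy (Arms 1+3 and Arms 2+4), which is the factor that splits the historical rates. SAP Section 2 is to be imported into the clinical study report. If the labels were reversed, a reader could set each radiation group beside the other group's historical rate, 18% in place of 33% or the reverse. The differing lower limit (4 or 5) and extracranial rate (53% or 49%) add to the impression that the report was transcribed carelessly.

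**Working it through.** **Inputs.** Crizotinib OIRR 18% (5 to 40) and 33% (13 to 59) from Protocol 10.9 and SAP 2.10; 18% (4 to 40) in 22 patients from Protocol 1.1.3 and 2.1; extracranial 53% and 49%, both with limits 43 to 63, from Protocol 1.1.3 and 2.1 respectively; planned OIRR limits from Protocol Table 10-3 (SAP Table 2-6).

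**Formula.** Exact (Clopper-Pearson) 95% limits for x responders in n: lower = 2.5% quantile of Beta(x, n-x+1); upper = 97.5% quantile of Beta(x+1, n-x).

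**Step 1: the plan's own figures.** 35/70 gives 37.80% to 62.20%; 30/50 gives 45.18% to 73.59%; 12/20 gives 36.05% to 80.88%. All agree with Table 10-3.

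**Step 2: which counts lie behind the historical rates.** All x/n with n from 3 to 300 were searched, rounding to whole percentages.

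| Printed figure | Counts that fit | Exact result |
|---|---|---|
| 18% (5 to 40) | 4/22 only | 18.2% (5.19 to 40.28) |
| 18% (4 to 40) | none | - |
| 33% (13 to 59) | 6/18 only | 33.3% (13.34 to 59.01) |

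The figure in 10.9 is therefore numerically 4/22, which matches the 22 patients in the background. That they are the same people is a fair inference but not proven: 10.9 gives no denominator, and the background prints a lower limit of 4, which no exact interval with 18% and 40 yields.

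**Step 3: the extracranial rate.** 58/109 = 53.2% (43.41 to 62.83), which fits 53% (43 to 63). For 49% the candidates are 53/109 = 48.6% (38.94 to 58.39) and 54/109 = 49.5% (39.82 to 59.28). Neither fits, and no x/n up to n = 399 gives 49% with 43 to 63. So 49% does not belong with its printed interval.

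**Step 4: what depends on the labels.**

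- The three lower bounds discussed in the text, 37.80%, 45.18% and 36.05%, exceed 18% and 33%. Exchanging the labels leaves that true.
- Some of the 13 rows in Table 10-3 have lower bounds under 33%: 26.41% (20/50), 31.81% (23/50), 27.20% (10/20) and 31.53% (11/20). All exceed 18%. Every row is either all of Arms 1-4 or a group defined by prior ALK inhibitor (Arms 1+2, Arms 3+4), so each pools irradiated and unirradiated patients. A radiation label cannot change how any row is read.
- The enrolment targets for measurable brain metastases (about 50 and 20) are also set by prior ALK inhibitor.
- The extracranial rate and the lower limit of 4 appear only in background text and enter no calculation.

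**The case for a change.** The best case for acting is that this is the only historical comparator printed beside the OIRR precision statements, that it is split by a factor used to report OIRR, and that the SAP text will pass into the study report. The remark about recent whole brain radiation, misplaced beside an unirradiated group, makes an exchange of labels plausible. A one-sentence correction looks cheap.

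Some of this stands. The sections are inconsistent, and 49% with limits 43 to 63 is a slip. It goes too far to say that the labels are reversed. Protocol 1.1.3 and 2.1 never define untreated as unirradiated, and the protocol elsewhere separates the state of a lesion from the history of the patient: under inclusion criterion 13, a new metastasis in a patient with previously treated brain metastases counts as active. The error could also lie in the background sections. The lower limit of 4 may have been printed that way in the report.

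Nor is a protocol correction as cheap as it looks. Section 12.1 requires a written amendment with ethics approval for any change, and enrolment ended in August 2017. The step that matters, checking the citation before the sentence is reused in the study report, is ordinary authoring work.

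**Conclusion.** The inconsistency is real but clerical, and no change to the plan follows. At its largest it is a 15-point difference (33% minus 18%) in the historical rate a reader might place beside each radiation group, and only if three assumptions hold: untreated means unirradiated, the two descriptions concern the same 22 patients, and the error lies in 10.9 and SAP 2.10 rather than in the background. The two rates rest on about 22 and 18 patients, with widely overlapping intervals (5 to 40 and 13 to 59), so even a correctly labelled informal comparison would be weak. The plan specifies no comparison with crizotinib. No test, sample size, confidence interval or planning statement uses either rate, and the trial's estimates would be the same under either labelling. The remaining differences (4 or 5; 53% or 49%) are background transcription points. All can be settled against the cited report when the study report is written.

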11.1 Regulatory and ethical compliance

This clinical study was designed, shall be implemented and reported in accordance with the ICH Harmonized Tripartite Guidelines for Good Clinical Practice, with applicable local regulations (including European Directive 2001/20/EC and US Code of Federal Regulations Title 21), and with the ethical principles laid down in the Declaration of Helsinki.

11.2 Responsibilities of the investigator and IRB/IEC/REB

The protocol and the proposed informed consent form must be reviewed and approved by a properly constituted Institutional Review Board/Independent Ethics Committee/Research Ethics Board (IRB/IEC/REB) before study start. Prior to study start, the investigator is

required to sign a protocol signature page confirming his/her agreement to conduct the study in accordance with these documents and all of the instructions and procedures found in this protocol and to give access to all relevant data and records to Novartis monitors, auditors, Novartis Clinical Quality Assurance representatives, designated agents of Novartis, IRBs/IECs/REBs and regulatory authorities as required.

[figure not shown]
11.3 Informed consent procedures

Eligible patients may only be included in the study after providing written (witnessed, where required by law or regulation), IRB/IEC/REB-approved informed consent

Informed consent must be obtained before conducting any study-specific procedures (i.e. all of the procedures described in the protocol). The process of obtaining informed consent should be documented in the patient source documents. The date when a subject's Informed Consent was actually obtained will be captured in their eCRFs.

Novartis will provide to investigators, in a separate document, a proposed informed consent form (ICF) that is considered appropriate for this study and complies with the ICH GCP guideline and regulatory requirements. Any changes to this ICF suggested by the investigator must be agreed to by Novartis before submission to the IRB/IEC/REB, and a copy of the approved version must be provided to the Novartis monitor after IRB/IEC/REB approval.

Women of child bearing potential should be informed that taking the study medication may involve unknown risks to the fetus if pregnancy were to occur during the study and agree that in order to participate in the study they must adhere to the contraception requirement for the duration of the study. If there is any question that the patient will not reliably comply, they should not be entered in the study.

[figure not shown]

11.4 Discontinuation of the study

Novartis reserves the right to discontinue this study under the conditions specified in the clinical study agreement. Specific conditions for terminating the study are outlined in [Section 4.4](#).

11.5 Publication of study protocol and results

Novartis is committed to following high ethical standards for reporting study results for its innovative medicine, including the timely communication and publication of clinical trial results, whatever their outcome. Novartis assures that the key design elements of this protocol will be posted on the publicly accessible database, e.g. www.clinicaltrials.gov before study start. In addition, results of interventional clinical trials in adult patients are posted on

www.novartisclinicaltrials.com, a publicly accessible database of clinical study results within 1 year of study completion (i.e., LPLV), those for interventional clinical trials involving pediatric patients within 6 months of study completion.

Novartis followed the ICMJE authorship guidelines (www.icmje.org) and other specific guidelines of the journal or congress to which the publications will be submitted.

Authors will not receive remuneration for their writing of a publication, either directly from Novartis or through the professional medical writing agency. Author(s) may be requested to present poster or oral presentation at scientific congress; however, there will be no honorarium provided for such presentations.

As part of its commitment to full transparency in publications, Novartis supports the full disclosure of all funding sources for the study and publications, as well as any actual and potential conflicts of interest of financial and non-financial nature by all authors, including medical writing/editorial support, if applicable.

For the Novartis Guidelines for the Publication of Results from Novartis-sponsored Research, please refer to www.novartis.com.

11.6 Study documentation, record keeping and retention of documents

Each participating site will maintain appropriate medical and research records for this trial, in compliance with Section 4.9 of the ICH E6 GCP, and regulatory and institutional requirements for the protection of confidentiality of subjects. As part of participating in a Novartis-sponsored study, each site will permit authorized representatives of the sponsor(s) and regulatory agencies to examine (and when required by applicable law, to copy) clinical records for the purposes of quality assurance reviews, audits and evaluation of the study safety and progress.

Source data are all information, original records of clinical findings, observations, or other activities in a clinical trial necessary for the reconstruction and evaluation of the trial. Examples of these original documents and data records include, but are not limited to, hospital records, clinical and office charts, laboratory notes, memoranda, subjects' diaries or evaluation checklists, pharmacy dispensing records, recorded data from automated instruments, copies or transcriptions certified after verification as being accurate and complete, microfiches, photographic negatives, microfilm or magnetic media, x-rays, and subject files and records kept at the pharmacy, at the laboratories, and medico-technical departments involved in the clinical trial.

Data collection is the responsibility of the clinical trial staff at the site under the supervision of the site Principal Investigator. The study case report form (eCRF) is the primary data collection instrument for the study. The investigator should ensure the accuracy, completeness, legibility, and timeliness of the data reported in the eCRFs and all other required reports. Data reported on the eCRF, that are derived from source documents, should be consistent with the source documents or the discrepancies should be explained. All data requested on the eCRF must be recorded. Any missing data must be explained. Any change or correction to a paper eCRF should be dated, initialed, and explained (if necessary) and should not obscure the

original entry. For electronic eCRFs an audit trail will be maintained by the system. The investigator should retain records of the changes and corrections to paper eCRFs.

The investigator/institution should maintain the trial documents as specified in Essential Documents for the Conduct of a Clinical Trial (ICH E6 Section 8) and as required by applicable regulations and/or guidelines. The investigator/institution should take measures to prevent accidental or premature destruction of these documents.

Essential documents (written and electronic) should be retained for a period of not less than fifteen (15) years from the completion of the Clinical Trial unless Sponsor provides written permission to dispose of them or, requires their retention for an additional period of time because of applicable laws, regulations and/or guidelines.

